5.1.3 Exploratory objectives

Compare the effect of 2x and 4 x treatments annually with PZQ to the standard 1x annual treatment on the Egg Reduction Rate (ERR)

Compare the effect of 2x and 4 x treatments annually with PZQ to the standard 1x annual treatment on the point prevalence.

Compare the effect of 2x and 4 x treatments annually with PZQ to the standard 1x annual treatment on the cure rate.

Estimate the efficiency of using infection intensity to predict the occurrence of AE's.

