8.6 Multiple Testing

(ICH E3; 9.7.1, 11.4.2.5. ICH E9; 2.2.5)

To allow for multiple testing of the primary endpoint and control for the type I error rate (false positive error rate) a gatekeeping procedure will be used. The null hypothesis of no difference in the prevalence of periportal fibrosis will be tested for each of the following comparisons and compared to a significance level (α – alpha) of 5%:

[figure not shown]
H₁: - 4 x annual treatment of PZQ v's Standard 1x annual treatment

H₂: - 2 x annual treatment of PZQ v's Standard 1x annual treatment

H₃: - 4 x annual treatment of PZQ v's 2 x annual treatment

Each hypotheses will be tested *in sequence* and testing continues until the null hypothesis cannot be rejected i.e. a non-significant result is obtained (Fig 2), or all three comparisons are statistically significant. The sequential testing rules mean that the overall rate of any false positive across the three possible comparisons is constrained to be less than 5% (11).

Fig 2: Flow diagram to illustrate testing of hypotheses using gate-keeping procedure

This is a deviation from the multiple testing approach detailed in the protocol v 2.0. The justification is to use the ordering implied by the details of the dosing: so if the most frequent dosing cannot show an improvement in efficacy compared to the least frequent, then we can assume the intermediate dosing will not do so either, and there would be no value in carrying out formal inference. This approach will help to maintain the power of the most relevant questions, given the anticipated reduction in sample size due to movement of the population as a result of the COVID 19 pandemic and other impactful local conditions.

9 Summary of Study Data

All continuous variables will be summarised using the following descriptive statistics: n (non-missing sample size), mean, standard deviation, median, maximum and minimum. The frequency and percentages (based on the non-missing sample size) of observed levels will be reported for all categorical

measures. In general, all data will be listed, sorted by treatment and subject, and when appropriate by visit number within subject. All summary tables will be structured with a column for each treatment in the order (Standard of Care, Intervention 1 (2 x treatment), Intervention 2 (4 x treatment) / Total) and will be annotated with the total population size relevant to that table/treatment, including any missing observations.

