The CR is the proportion of participants who have changed from an epg >0 to and epg of =0 between timepoints;

 $CR = \frac{Total\ number\ of\ participants\ who\ have\ an\ average\ epg\ =\ 0\ at\ timepoint\ 1}{Number\ of\ participants\ who\ have\ epg\ >\ 0\ at\ timepoint\ 0}$

Residency in Holma district is dichotomised into 2 years - 4 years/ > 4 years

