9.6 Withdrawals

Listings of withdrawals from the trial (ordered by withdrawal reason) will be produced and will consist of the following variables:

- Subject ID
- Treatment group
- · Withdrawal reason
- School
- Gender
- Age

Time to withdrawal (days).

Summary statistics of the:

- withdrawal reason
- school
- gender
- age

will be produced according to section 9 using the safety population.

10 Efficacy Analysis

The primary and secondary efficacy analysis will be analysed using the full analysis population.

The following information will be summarised according to section 9 for the 24 months and 24 months +4 weeks follow up visits using the full analysis population. Box and whisker plots will be used to display continuous endpoints and stacked bar charts to represent binary and categorical endpoints.

- Niamey Protocol pattern score: (A /B /C / D / E //F)*
- Periportal fibrosis: (Yes / No) derived variable see section 9.2
- Infection intensity: EPG derived variable see section 9.2
- Infection intensity: Heavy infection derived variable see section 9.2
- Infection intensity ERR derived variable see section 9.2
- Infection: Point Prevalence derived variable see section 9.2
- Cure Rate derived variable see section 9.2

*Niamey Protocol pattern score will only be presented for the 24 month time point

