10.2.2 Analysis of secondary endpoint – Infection intensity (mean epg)
Analysis of the secondary endpoint will test if there is a difference in the mean infection intensity between the control and each intervention arm as well as between each of the two intervention arms.

A multiple linear regression model will estimate the infection intensity at 24 months for each treatment group adjusted for baseline infection intensity (EPG), and school. A z-test will compare each of the three pairwise comparisons separately and provide a p-value for the probability that a difference in the means produced by the model would be observed purely due to chance.

Note that an additional analysis was added post hoc which modelled the mean infection intensity by treatment group which adjusted for baseline infection intensity and school with an interaction term between treatment group and school.

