10.2.3 Analysis of secondary endpoint – Infection intensity (Heavy infection)

An additional analysis of the infection intensity endpoint will be conducted by dichotomising EPG into ≥400 EPG or <400 EPG relating to 'heavy infection' and 'not heavy infection'. The analysis will estimate the proportion of 'heavy infection' for each treatment arm by fitting a logistic regression model and adjusting for baseline infection intensity (epg), and school. 95% confidence intervals for the proportions will be estimated using the standard error from the model.

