10.2.6 Analysis of secondary endpoint - Cure rate

The cure rate as defined in section 9.2 will be calculated for the following time points:

- Baseline to 24 months
- Baseline to baseline +4 weeks
- 24 months to 24 months + 4 weeks

Cure rates will be presented by treatment arm and also stratified by baseline infection intensity; \geq 400 epg = Heavy infection / <400 - 1 epg = Medium - Light Infection.

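### Cure rate carries an exploratory objective to compare treatment frequencies, but its planned analysis gives only proportions by arm, with no between-arm estimate or interval

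*SAP*

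**What the plan says.** The objective in SAP 5.1.3 is comparative: "Compare the effect of 2x and 4 x treatments annually with PZQ to the standard 1x annual treatment on the cure rate". It stands under exploratory objectives, and 5.2.2 lists cure rate among the exploratory endpoints, although the heading of 10.2.6 calls it secondary.

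SAP 9.2 defines the quantity: "The CR is the proportion of participants who have changed from an epg >0 to and epg of =0 between timepoints". For the analysis, 10.2.6 says "The cure rate as defined in section 9.2 will be calculated for the following time points", names three pairs of visits, and continues: "Cure rates will be presented by treatment arm and also stratified by baseline infection intensity", with the split at 400 epg.

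Cure rate is also in the list that opens section 10, where "The following information will be summarised according to section 9 for the 24 months and 24 months +4 weeks follow up visits". The section 9 convention for categorical measures is "The frequency and percentages (based on the non-missing sample size) of observed levels will be reported for all categorical" measures.

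Other infection endpoints get more. For mean epg (10.2.2), "A z-test will compare each of the three pairwise comparisons separately". For heavy infection (10.2.3), "95% confidence intervals for the proportions will be estimated using the standard error from the model". Egg reduction rate has a mixed model (10.2.4) and 24-month prevalence has an adjusted odds ratio (10.2.5).

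**The concern.** An objective to compare arms needs an estimate of how far they differ and how precisely that is known. Percentages by arm and by intensity stratum give neither, so a reader cannot tell an effect of treatment frequency from sampling variation.

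The three intervals in 10.2.6 are also presented alike, although they do not support the same comparison. Only baseline to 24 months starts from a group fixed before treatment differs and then spans the period in which it does differ. At stake is whether an exploratory objective is answered and whether its table is over-read.

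**Working it through.** **1. Where a comparison of cure could be found in the SAP**

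| Place | What it gives for cure |
|---|---|
| 10.2.6 | Rates by arm and by baseline intensity stratum |
| Opening of section 10, using section 9 | Frequencies and percentages |
| 10.2.7 | Alluvial plots of epg status, by arm and overall |
| 10.3.1 (CACE) | Nothing: covers the primary outcome, mean epg and heavy infection |
| 10.2.5 | A model of epg > 0 at 24 months among all with a result, not a model of cure |

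None gives a between-arm estimate or an interval for cure. Egg reduction rate and prevalence, listed as exploratory alongside cure in 5.1.3, both get a model. So the omission does not follow from a general rule for exploratory endpoints.

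**2. What each interval can show**

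- Baseline to baseline + 4 weeks: by the schedule in 9.5, the first dose that differs between arms is at month 4. If doses are on schedule, this interval cannot show an effect of frequency.
- Baseline to 24 months: the denominator is infection at baseline, before treatment differs. This allows a randomised contrast, subject to loss to follow-up.
- 24 months to 24 months + 4 weeks: the denominator is children infected after up to two years of differing treatment. It is a post-randomisation group.

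**3. Size**

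The SAP states no figure for cure rate. Its only design calculation is for the primary endpoint, and it reproduces. For 80% v 60%, 100 per arm, two-sided 5%, pooled variance: z = (0.20 × √100 − 1.96 × √(2 × 0.7 × 0.3)) / √(0.16 + 0.24) = (2 − 1.270) / 0.632 = 1.154. This gives 87.6% power, against the stated 88% (section 7). The point does not rest on this figure.

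For cure, all inputs are assumptions: 60 to 80 baseline-infected children per arm with a 24-month result, 30 to 40 per arm within an intensity stratum, and a true cure rate p of 20% or 50%, equal in both arms.

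- SE of a difference = √(2p(1 − p)/n)
- 95% half-width = 1.96 × SE
- Chance of a gap of 10 points or more with no true effect = 2 × (1 − Φ(0.10/SE))

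| n per arm | p | SE | Half-width (points) | Chance of gap ≥ 10 points |
|---|---|---|---|---|
| 80 | 0.2 | 0.063 | 12.4 | 11% |
| 80 | 0.5 | 0.079 | 15.5 | 21% |
| 60 | 0.2 | 0.073 | 14.3 | 17% |
| 60 | 0.5 | 0.091 | 17.9 | 27% |
| 40 | 0.2 | 0.089 | 17.5 | 26% |
| 40 | 0.5 | 0.112 | 21.9 | 37% |
| 30 | 0.2 | 0.103 | 20.2 | 33% |
| 30 | 0.5 | 0.129 | 25.3 | 44% |

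A wider set of assumptions (25 to 100 per arm, cure 30% to 70%) gives half-widths of 12.7 to 27.7 points and chances of 12% to 48%.

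**4. Two inconsistencies in the same text**

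- The sentence in 9.2 counts children who change from infected to uninfected. The numerator of the formula below it counts everyone with epg = 0 at the later visit, including any who were already at zero.
- For the third pair of visits, 5.2.2 lists baseline to 24 months + 4 weeks, whereas 10.2.6 lists 24 months to 24 months + 4 weeks.

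**The case against.** The strongest reply has four parts.

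- **The endpoint is exploratory.** No alpha, power statement or primary conclusion depends on it, and reporting such an endpoint as proportions is defensible. This stands as to weight: no formal test is needed. It does not remove the mismatch with an objective worded as a comparison. Rewording the objective as descriptive would remove the mismatch, but would leave the question unanswered when the data and most of the method are already in the plan.
- **Section 10.2.5 already models infection status at 24 months.** It adjusts for age, sex and school, and a post hoc version adds baseline ln(epg+1). A reader might infer that any conclusion on cure would rest on comparing raw percentages by eye. The overlap with 10.2.5 means the SAP does not support that. But the model takes in children uninfected at baseline, so it would come close to the cure contrast only if nearly all were infected then, which the SAP does not state.
- **Section 10.2.6 does stratify by baseline intensity.** So it would be wrong to say baseline intensity is ignored. The split is coarse, and it yields no adjusted comparison.
- **A descriptive table suits two of the three intervals.** This stands. The gap in inference is confined to baseline to 24 months.

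**Conclusion.** The point holds as a modest one. A comparative exploratory objective ends in a table without a between-arm estimate or interval, and the prevalence model replaces it only in part. On the assumed inputs, a difference in cure would carry a 95% half-width of about 12 to 18 points overall and about 18 to 25 points within strata. With no true effect, a gap of 10 points or more between two arms would arise about 11% to 27% of the time overall and about 26% to 44% within strata.

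A reader might go further and infer that such gaps are to be expected by chance. The figures do not support that: for any given pair of arms the probability is below one half throughout. Such gaps are common enough that bare percentages can mislead, and no more than that. Nor is there any consequence for the primary analysis.

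The ranges rest on assumed numbers infected and assumed cure rates, since the SAP states neither.

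**What to change.** In SAP 10.2.6:

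- For baseline to 24 months, restrict to children with epg > 0 at baseline. Fit a logistic model with arm, school and baseline ln(epg+1). Report the standardised risk difference with 95% CI for 4x v 1x and 2x v 1x, by the g-formula and bootstrap already described in 10.1. Label it exploratory, and post hoc if it is added after data were seen. State whether children whose baseline egg count is imputed under 8.4.2 enter the denominator.
- Give 95% CIs for the other cure rates and label them descriptive, with the reason: baseline to + 4 weeks precedes the first arm-specific dose in the 9.5 schedule, and 24 months to + 4 weeks has a post-randomisation denominator.

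In the same edit, limit the numerator of the 9.2 formula to children with epg > 0 at timepoint 0, and reconcile the cure-rate time points in 5.2.2 and 10.2.6.

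The cost is SAP wording and one model that can reuse the 10.1 method. The downside is one more exploratory analysis with wide intervals, possibly one more with a post hoc label beside those already recorded in 16.1.5.

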10.2.7 Alluvial plots

Alluvial plots will be produced to show changes in the proportions of participants who have epg > 0 and epg = 0 over time for:

- · All participants combined
- · Each treatment group separately

Alluvial plots will also be produced to show changes in the proportions of participants who have Heavy infection (epg >400) over time.

- All participants combined
- Each treatment group separately

10.3 Exploratory Efficacy Analyses

10.3.1 Complier Average Causal Effect analysis

To investigate how treatment compliance affects the primary outcome CACE (Complier Average Causal Effect) analysis will be performed (17) to compare each intervention arm separately to the control arm.

The CASE will be calculated using the ITT treatment effect and the proportion of compliers in the treatment arms, different levels of compliance will be used and are defined below for each intervention arm:

Intervention arm 1: Participants who take ≥ 4 doses of the PZQ out of a maximum of 5 possible doses.

Intervention arm 2: Participants who take ≥ 8 doses of the PZQ out of a maximum of 9 possible doses.

AND

Intervention arm 1: Participants who take > the baseline i.e. the control arm dose of PZQ (2 doses)

Intervention arm 2: Participants who take > intervention arm 1 dose of PZQ i.e. 5 doses

CASE calculation:

Intention To Treat (ITT) treatment effect
proportion of compliers in the intervention arm

The CACE estimation relies on the following assumptions:

- Treatment assignment is random
- Merely being offered the treatment has no effect on the outcomes
- If participants in the control arm had been randomised to the intervention arm, they would comply with the intervention at the same rate as those actually randomised to the intervention
- There is an absence of defiers patients that take the opposite treatment to what is offered
- Stable Unit Treatment Value Assumption (SUTVA). SUTVA requires that the response of a particular participant depends only on the treatment to which the participant was assigned, not the treatments of others.

If these assumptions hold we can also estimate the potential outcomes among participants in the control arm using simple algebra.

'Complier' and 'Non-complier refer specifically to compliance to the intervention and participants in the control arm are assumed to receive the control treatment as intended and values therein are based on the aforementioned assumptions.

This analysis will also be performed for the secondary outcome of infection intensity:

- o mean epg
- Heavy infection

11 Safety Analyses

The safety population will be used for all safety analysis.

Safety data collected on the day of treatment and at 24 hours will be grouped for each time point, i.e. AE's from day 1 and \pm 24 hours will be grouped for baseline AE's and any repetitions will not be counted within the time-point.

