9.5 Treatment Compliance

Information relating to the number of participants who missed the IMP at the required visit captured in the 'Non-Adherence to protocol' CRF as well as the 'IMP administration' CRF will be shown in a summary table and displayed as a stacked bar chart, each treatment group represented by their colour and position within the stack. The number missing will be a scale on the y axis and each treatment time—point will be ordered on the x axis.

- · Standard of Care Arm: Baseline, 12 months and 24 months
- Intervention Arm 1 (2 x treatment): Baseline, month 7, month 12, month 19 and month 24
- Intervention arm 2 (4 x treatment): Baseline, month 4, month 7, month 10, month 12, month 16, month 19, month 22 and month 24

Information relating to the number of participants who missed data collection visits captured in the 'Non-Adherence to protocol' CRF will be shown in a summary table and displayed using a stacked bar chart with each treatment arm represented by their colour and position within the stack, the number missing will be shown on the y axis and time-point on the x axis.

- Ultrasonography
- Parasitology
 - Standard of Care Arm: Baseline and 24 months
 - o Intervention Arm 1: Baseline and 24 months
 - o Intervention arm 2: Baseline and 24 months

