16.1.2 Change to definition of Full Analysis population

Removal of the condition to only include participants 'treated at baseline' in the population. Due to the COVID 19 pandemic many participants were not treated at baseline but were treated at other time points in the trial. Including only participants treated at baseline would significantly reduce the sample size and reduce the power. Also information would be lost for those participants not treated at baseline but treated at other time points

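### The complier rules for the CACE analysis count the month-24 dose in the intervention arms but not in control, and dividing by the complier share ignores partial dosing, with a bias that differs by rule

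*SAP*

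**What the plan says.** Section 9.5 of the SAP lists the dosing points:

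- Control: "Standard of Care Arm: Baseline, 12 months and 24 months".
- Arm 1: "Intervention Arm 1 (2 x treatment): Baseline, month 7, month 12, month 19 and month 24".
- Arm 2: "Intervention arm 2 (4 x treatment): Baseline, month 4, month 7, month 10, month 12, month 16, month 19, month 22 and month 24".

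Section 10.3.1 estimates the CACE as the ITT effect divided by the share of compliers in the intervention arm, under two levels of compliance per arm. The strict rules are "Participants who take ≥ 4 doses of the PZQ out of a maximum of 5 possible doses" for arm 1 and, for the other arm, "Intervention arm 2: Participants who take ≥ 8 doses of the PZQ out of a maximum of 9 possible doses". The loose rules are "Intervention arm 1: Participants who take > the baseline i.e. the control arm dose of PZQ (2 doses") and, for arm 2, more than the arm 1 count, which is given as 5.

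The section assumes that an offer of treatment has no effect by itself, and that "participants in the control arm are assumed to receive the control treatment as intended". Doses taken below a threshold are not mentioned. Section 16.1.2 reports that "many participants were not treated at baseline but were treated at other time points in the trial".

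The analysis is applied to periportal fibrosis, mean epg and heavy infection. The fibrosis and egg-count endpoints are measured at 2 years (sections 5.2.1 and 5.2.1.1).

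**The concern.** There are two separate problems.

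**Counting.** The rules use one convention for control and another for the intervention arms. The dose that makes the difference is given at the outcome visit, so complier status depends partly on something that cannot have influenced the outcome.

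**Estimator.** Dividing by the complier share is valid only if allocation changes nothing for those classed as non-compliers. Here compliance is graded: a child can take several extra doses and still fall below the line. Section 16.1.2 shows that incomplete dosing did occur.

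This is the SAP's only analysis of how compliance relates to outcome. If the bias differs in size and sign across the four rules, the four estimates cannot be compared, and a difference between them could be read as a dose-response when it comes from the definitions.

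**Working it through.** **1. Dose counts**

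| | Control | Arm 1 | Arm 2 |
|---|---|---|---|
| Section 9.5, all dosing points | 3 | 5 | 9 |
| Section 9.5, before month 24 | 2 | 4 | 8 |
| Used in section 10.3.1 | 2 | 5 | 9 |

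A consistent count is 3/5/9 or 2/4/8; section 10.3.1 has 2/5/9. The 24-month stool is the pre-dose sample for the egg reduction rate (5.2.2) and cure rate (10.2.6) from 24 months to 24 months + 4 weeks, so the month-24 dose comes after the outcome egg count.

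**2. A child dosed only at baseline, 12 and 24 months (3 doses)**

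- Arm 1, more than 2: 3 > 2, complier.
- Arm 1, at least 4: not a complier.
- Arm 2, at least 8: not a complier.
- Arm 2, more than 5: not a complier.

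Under the first rule, 16 of the 32 possible dose patterns qualify. Of these, 6 contain only 2 doses before the outcome, the same number as control.

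**3. What the ratio estimates**

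Let p be the complier share, and Ec and En the mean effect of allocation in compliers and non-compliers. Then

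ITT = p·Ec + (1 − p)·En, so ITT/p = Ec + [(1 − p)/p]·En.

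The second term is the bias. It is positive when non-compliers took more effective doses than they would have under control, and negative when they took fewer.

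**4. Size, under assumptions**

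The SAP gives neither uptake nor a dose-response. Assume independent visits with the same uptake, an effect of d per dose before month 24, and control fully adherent at 2 such doses (the SAP's own assumption).

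Arm 2, at least 8 of 9, uptake 0.8:
- p = 9 × 0.8^8 × 0.2 + 0.8^9 = 0.302 + 0.134 = 0.436
- ITT = (8 × 0.8 − 2)d = 4.4d
- ITT/p = 4.4d/0.436 = 10.09d
- Mean total doses in compliers = (8 × 0.302 + 9 × 0.134)/0.436 = 8.31. Of these, 8/9 (7.38) fall before month 24, so Ec = 5.38d
- Ratio = 10.09/5.38 = 1.87

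The largest possible contrast is 8 − 2 = 6 doses, so an estimate of 10.09d exceeds even the effect of complete dosing.

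Arm 1, more than 2, uptake 0.8:
- p = 0.205 + 0.410 + 0.328 = 0.942
- ITT = (4 × 0.8 − 2)d = 1.2d
- ITT/p = 1.274d
- Mean total doses in compliers = 4.13. Of these, 4/5 (3.30) fall before month 24, so Ec = 1.304d
- Ratio = 1.274/1.304 = 0.98

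Ratio of ITT/p to the true complier effect, control fully adherent:

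| Rule | 0.6 | 0.7 | 0.8 | 0.9 |
|---|---|---|---|---|
| Arm 1, ≥4 | 0.86 | 1.04 | 1.05 | 1.02 |
| Arm 1, >2 | 0.66 | 0.90 | 0.98 | 1.00 |
| Arm 2, ≥8 | 7.6 | 3.5 | 1.9 | 1.2 |
| Arm 2, >5 | 1.48 | 1.18 | 1.04 | 1.00 |

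If children would miss the baseline and 12-month visits equally under control, the rows become: arm 1 ≥4, 2.1/1.5/1.2/1.06; arm 1 >2, 1.22/1.09/1.03/1.00; arm 2 ≥8, 9.4/3.9/2.0/1.2; arm 2 >5, 1.7/1.2/1.06/1.01.

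**5. Direction of the counting error**

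For arm 1 >2, leaving month 24 out changes the complier share and the multiplier 1/p as follows:

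| Uptake | p, counted | p, not counted | 1/p, counted | 1/p, not counted |
|---|---|---|---|---|
| 0.6 | 0.68 | 0.48 | 1.46 | 2.10 |
| 0.7 | 0.84 | 0.65 | 1.20 | 1.53 |
| 0.8 | 0.94 | 0.82 | 1.06 | 1.22 |
| 0.9 | 0.99 | 0.95 | 1.01 | 1.05 |

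The present count therefore pulls this estimate toward the ITT effect.

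**The case against.** A reader might infer that the whole CACE analysis overstates the effect of compliance. The document does not support that. Counting month 24 and the loose arm 1 rule both enlarge the complier share, which shrinks the estimate. Under the SAP's own assumption of full control adherence, the arm 1 >2 estimate is at or below the true complier effect.

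A single figure for the overstatement would also mislead. Suppose half of arm 2 took 8 doses before month 24 and half took 6, and all were dosed at month 24. ITT is 0.5 × 6d + 0.5 × 4d = 5d. The ≥8 rule gives 5d/0.5 = 10d against a true 6d, which is 67% too high. Under the >5 rule every child is a complier, p = 1, and the estimate of 5d is exact. Both results would be reported.

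Further points stand against a stronger reading:

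- The control-schedule misclassification affects one rule of four.
- Full control adherence is a declared assumption. It is open to doubt given section 16.1.2, but it is not concealed.
- The analysis is exploratory and outside the gatekeeping sequence. Dividing by p rescales the ITT effect and cannot change its sign.
- A per-dose estimate answers a different question and adds a linearity assumption, so it is not needed to correct the counts.

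None of this removes the mixed convention in 10.3.1 or the failure of the exclusion restriction when partial doses work.

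**Conclusion.** The point holds in two parts. First, sections 9.5 and 10.3.1 disagree on dose counts, and the thresholds for the intervention arms include a dose that cannot affect the 24-month outcomes. This follows from the text alone. Second, the ratio is biased whenever doses below the threshold have an effect. The overstatement is marked for arm 2 ≥8 (about 1.2 to 7.6 times at uptake of 0.9 to 0.6) and smaller for arm 2 >5. For arm 1 >2 there is little bias or an understatement.

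The sizes rest on assumed uptake, independent visits, a linear effect of doses before month 24 and full control adherence. If control children also miss visits, the arm 1 ratios rise to 1 or above, so the sign for arm 1 is not settled by the document. The primary result is unaffected. The correction is still worthwhile, because the rules as written would give estimates that cannot be compared across arms or thresholds.

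**What to change.** 1. Reconcile the dose counts in sections 9.5 and 10.3.1.
2. For this analysis, define compliance in every arm by doses received before the 24-month ultrasound and stool collection, and restate all four thresholds on that basis.
3. State in 10.3.1 that the binary-threshold CACE is biased when partial doses have an effect, and that the bias can differ between rules.
4. Add, without necessarily replacing the CACE, an instrumental-variable estimate. Allocation is the instrument and the number of pre-outcome doses actually received, in control as well, is the exposure. For each comparison this is the ITT effect divided by the between-arm difference in mean doses, with a bootstrap confidence interval. State that it estimates an average effect per dose and assumes rough linearity.

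The cost is SAP wording and modest programming. Dose data are already on the IMP administration CRF named in section 9.5. Item 4 uses received doses in all arms, so it does not need the assumption that control children took every dose.
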